### **5.2 Randomization and blinding**

Clinics will be randomized to treatment arms in equal proportions. We will use clinic-based cluster randomization to minimize the possibility of contamination in study interventions between practices and clinic staff. For the randomization, we will use covariate constrained randomization in R software based on clinic characteristics to reduce potential imbalances between the clinics assigned to the treatment arms. The clinics/providers will not be blinded to which arm they were assigned to, as blinding in the context of an intervention that is intended to motivate action will be infeasible. Physicians randomized to usual care will not have any way of accessing the EHR interventions. Patients of physicians in the usual care arm will have access to the patient portal but will not be receiving any assistance from medical assistants or any of the after-visit activities. Moreover, only primary care physicians will be included (specialists will not receive any enhanced clinical decision support or report cards), and feasibility data suggest that there is minimal crossover of patients with other primary care physicians given the nature hypertension management at Advocate. Therefore, any risk of contamination within practices is low, and any contamination that does exist would bias the trial results towards the null.

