### **6.5 Study endpoints**

The trial will be completed 24 months after trial launch. At the end of the study period, data will be extracted retrospectively from electronic health records; the primary analysis will be on patients who visited one of the 24 clinics during the study period and who meet the inclusion criteria.

Primary:

- Change in systolic blood pressure from patient identification (i.e., the most recent encounter that identified the patient as eligible) through 12-month follow-up, using values recorded in the EHR

Secondary:

- Percentage of patients with well-controlled blood pressure (<140/88mmHg) or <130/80 mmHg for those with comorbid conditions defined by clinical guidelines at 12 months follow-up, using values in the EHR
- Percentage of patients with intensification of medication in the 12-month follow-up period, defined by addition of therapy or increasing dose
- Percentage of patients with guideline-concordant medications ordered in the 12-month follow-up period
- Change in the gap in systolic blood pressure between each of Black and Hispanic/Latino patients and non-Hispanic White patients from the last encounter before identification through 12 months after, using values in the EHR
- Change in diastolic blood pressure from the encounter before identification through 12 months after, using values recorded in the EHR

Exploratory:

- Frequency of viewing the dashboard, SmartSet order set, documentation choices, and acknowledgement reasons
- Intervention fidelity: BPAs (alerts) firing as intended

Clinical encounters, using number of office visits, telephone calls and patient portal interactions between AAH primary care providers and patients during the 12-month follow-up period. These outcomes will also be measured in the remainder of the follow-up period until the end of administrative censoring at the end of the 2-year trial.

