### 9.2. Sample size determination

We powered the study to detect a 5.0 mmHg mean change in SBP between the intervention arm and control arm from randomization through 12 months, assuming a standard deviation (SD) of 13.5, an alpha threshold of 0.05, and an intra-cluster correlation (ICC) of 0.1. With these assumptions, we estimated that at least 24 eligible primary care clinics including 537 providers and 49395 patients that were identified as eligible for inclusion in the analysis will provide >80% power to detect differences in our primary outcome. The 5.0 mmHg mean change was chosen as this is considered to a clinically meaningful change in SBP and was observed in prior systematic reviews of interventions in hypertension. This estimate also accounts for regression to the mean and includes SDs that were derived from our prior work and Advocate feasibility data.

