### 9.3. Analyses of endpoints

Descriptive statistics will be calculated for all variables and presented overall and by group using mean + SD for continuous variables, as well as counts or percentages for categorical variables. Comparisons will be made between groups for all outcomes using absolute standardized differences. The unit of analysis is at the patient-level.

For the primary outcome, we will use generalized estimating equations (GEE) to adjust for the cluster design with an identity link function and normally-distributed errors. If >10% of data is missing, we will use multiple imputation for our study outcomes, as we have done in prior research. We will test the robustness of this approach with sensitivity analyses that use alternative methods of handling missing data. For baseline characteristics between arms with a standardized difference >0.1, we will repeat our analyses after adjusting for these covariates. We will also conduct analyses by racial/ethnic subgroup. In secondary analyses, we will also use longitudinal modeling to account for multiple SBP values over follow-up.

For secondary outcomes, we hypothesize that the intervention will lead to more patients with well-controlled blood pressures, higher rates of treatment intensification and guideline concordance. The null hypotheses will be no difference between the intervention arm and usual care. For these outcomes, we will use GEE with an identity link and normally-distributed errors for continuous variables and with a log-link function and Poisson-distributed errors for categorical variables. For outcomes that are non-normal, we will use GEE with a log-link function and Poisson-distributed errors, as in our prior work. For all primary and secondary outcomes, the study analysts and investigators will be blinded to treatment allocation until after the analyses are complete. We will also evaluate other implementation outcomes, including clinical outcomes past the initial 12 month follow-up, until 24 months (i.e., the end of the trial), to explore durability of treatment effects.

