De-identified qualitative interview transcripts (interviews previously conducted under the IRB approval of Advocate Aurora Health) will be analyzed using immersion-crystallization methods using Dedoose qualitative software (SocioCultural Research Consultants, LLC). In this approach, we immerse ourselves in the collected data and then articulate the salient themes during the crystallization process. We will continue this approach of cycles of concentrated textual review until all data are examined, and meaningful patterns emerge from the data. Collected data will be used to describe and understand both patient and providers perspectives on hypertension management.

Because this is a randomized trial, our primary analyses are planned as unadjusted; however, if there are strong patient-level predictors of the outcomes not balanced by stratified randomization, we will adjust for these in the primary analyses.

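### Section 9.3 does not fix one primary model: adjustment enters the primary analysis on an imbalance trigger that is never defined

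*Combined protocol and SAP*

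**What the plan says.** The primary endpoint (section 6.5) is "Change in systolic blood pressure from patient identification (i.e., the most recent encounter that identified the patient as eligible) through 12-month follow-up". For it, section 9.3 states that "we will use generalized estimating equations (GEE) to adjust for the cluster design with an identity link function and normally-distributed errors"; that description names no covariate.

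Section 9.3 then deals with imbalance twice.

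- In the paragraph on the primary outcome: "For baseline characteristics between arms with a standardized difference >0.1, we will repeat our analyses after adjusting for these covariates".
- In its last paragraph: "our primary analyses are planned as unadjusted; however, if there are strong patient-level predictors of the outcomes not balanced by stratified randomization", with the consequence that "we will adjust for these in the primary analyses".

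On allocation, section 5.2 says "we will use covariate constrained randomization in R software based on clinic characteristics to reduce potential imbalances between the clinics". The same part of section 9.3 that sets out the outcome models provides that "the study analysts and investigators will be blinded to treatment allocation until after the analyses are complete".

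**The concern.** The default is clear: an unadjusted primary GEE. The exception is not. The closing clause gives no threshold for a strong predictor or for lack of balance, lists no covariates, and does not refer to the 0.1 threshold given earlier. A strong predictor with a standardized difference above 0.1 meets both rules. One makes the adjusted result an addition to the primary result, and the other makes it the primary result. Two competent analysts who follow the plan could therefore report different primary estimates.

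The clause also refers to stratification, but section 5.2 describes a constrained scheme and no stratification factor appears in the available text. The constraint acts on clinic characteristics, while the clause concerns patient-level predictors. No available text carries the constrained characteristics into the primary model.

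This deserves attention because only 24 clinics are randomized. A large number of patients does not guarantee patient-level balance, and with change in SBP as the outcome, baseline SBP is an obvious candidate for a strong predictor.

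**Working it through.** **1. The plan's own power.** Section 9.2 gives 24 clinics, 49,395 patients and a 5.0 mmHg difference, "assuming a standard deviation (SD) of 13.5, an alpha threshold of 0.05, and an intra-cluster correlation (ICC) of 0.1".

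- Mean clinic size: 49,395/24 = 2,058.
- SE = 13.5 × sqrt((0.1 + 0.9/2058)/6) = 1.75 mmHg.
- Power, two-sided normal approximation: 5/1.75 = 2.86, giving 81.7%. This reproduces the stated figure of more than 80%.
- With a t reference on 22 df, the same inputs give 78.1%. The comparisons below use that reference throughout.

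**2. Gap between the two candidate estimates.** The worked covariate is baseline SBP. The documents give neither its SD, its ICC nor its slope, so these are assumptions: SD 13.5; ICC 0.01, 0.05 or 0.10; slope of change on baseline -0.3, -0.5 or -0.7; baseline SBP not among the constrained variables.

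- A standardized difference of exactly 0.1 is 0.1 × 13.5 = 1.35 mmHg.
- Shift in the estimate = size of slope × 1.35 = 0.41, 0.68 or 0.95 mmHg. That is 8%, 14% or 19% of 5 mmHg, and 0.23, 0.39 or 0.54 of the SE.

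**3. How often the threshold is exceeded.** For baseline ICC ρ, the SD of the standardized difference is sqrt((ρ + (1 - ρ)/2058)/6) = 0.042, 0.092 or 0.129. The chance of exceeding 0.1 in either direction is 1.7%, 28% or 44%.

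**4. How often the choice changes the conclusion.** Clinic means were simulated (12 v 12, slope taken as known, t with 22 df, 100,000 runs per scenario), with the clause applied mechanically at 0.1. Ranges run over the three slopes. The fourth column is the product of the second and third.

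| Baseline ICC | Difference >0.1 | Models disagree on p<0.05 at 5 mmHg, among those trials | Same, among all trials | Type I error of conditional rule | Power if always adjusted |
|---|---|---|---|---|---|
| 0.01 | 1.7% | 7.1-17.5% | 0.1-0.3% | 5.0% | 78.8-80.0% |
| 0.05 | 28% | 9.5-22.3% | 2.7-6.2% | 3.9-4.7% | 80.0-88.2% |
| 0.10 | 44% | 11.4-27.7% | 5.0-12.2% | 2.8-4.5% | 81.9-97.0% |

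Unadjusted power is 78%. Power under the conditional rule is 78-89%.

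**5. Adding the constrained clinic variables.** A further simulation assumed four such variables, an allocation drawn from the best 10% of 300, baseline ICC 0.05, slope -0.5, a Kauermann-Carroll variance and 18 df (24 clinics minus intercept, arm and four covariates), with 6,000 runs.

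| Between-clinic variance explained | Unadjusted: power (type I) | Baseline SBP only: power | Baseline SBP and clinic variables: power (type I) |
|---|---|---|---|
| 0% | 77.9% (4.7%) | 82.9% | 80.7% (5.3%) |
| 10% | 78.4% (4.1%) | 84.2% | 85.0% (5.0%) |
| 30% | 80.4% (2.5%) | 86.0% | 93.9% (5.2%) |
| 50% | 83.2% (1.2%) | 89.2% | 98.9% (5.2%) |

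If the constrained variables are prognostic, the unadjusted test is conservative, because its standard error does not reflect the balance achieved.

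A patient-level GEE check (400 patients per clinic, 1,500 runs, ICC 0.05, slope -0.5) gave power of 77.5% unadjusted and 82.8% with baseline SBP. Type I error was 4.7% and 6.1%, with a Monte Carlo error of 0.6 points.

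**The case against.** The best defence is that the two paragraphs are a general rule and an exception: strong imbalanced predictors enter the primary model, and every other imbalanced covariate prompts a repeat analysis. The text allows this reading, so it goes too far to call the rules flatly incompatible. But the plan does not state it, and with the trigger undefined it still does not fix one model.

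Blinding of analysts and investigators limits choosing a model by its result. That stands, but blinding does not say which model is primary.

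A reader might draw four stronger conclusions that the documents do not support.

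- *That the clause inflates the false-positive rate.* Applied mechanically it gave 2.8-5.0%. Only if either estimate could be claimed as primary did a separate null simulation (20,000 runs, one covariate, correlation 0.3 or 0.5) reach 4.8-6.2%, and the blinding provision works against that.
- *That the clause costs power.* It does not, relative to the plan's default. The shortfall is only against a model that always adjusts.
- *That the 78% shows an error in section 9.2.* It reflects the t reference. The normal approximation supports the stated power.
- *That imbalance is likely in this trial.* The trigger rates assume that baseline SBP is unconstrained. If clinic mean SBP were one of four constrained variables, they would fall to about 0%, 0.1% and 6%; if one variable correlated 0.7 with it, to about 0.1%, 15% and 32%. The available text does not list the variables.

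The stratification wording is a slip with no analytic effect of its own, because section 5.2 states the method.

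**Conclusion.** The point stands as an ambiguity in the primary analysis. If no strong predictor is imbalanced, the primary model is plainly unadjusted. If one is, the covariates in the primary model depend on the data and on an undefined judgement. That conclusion rests on the text alone.

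The size rests on the assumed baseline SD, ICC and slope, on a clinic-level slope equal to the patient-level slope, and on baseline SBP being unconstrained. It is negligible at a baseline ICC of 0.01, reaches about 12% of trials at the top of the assumed range, and is smaller if clinic SBP was constrained. This should be corrected because it is cheap to do so; it does not threaten the validity of the trial.

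**What to change.** Pre-specify one primary model whatever balance is observed: a GEE of change in SBP on arm, individual baseline SBP and a short named list of the clinic variables used in the constrained randomization. Use a small-sample variance correction (for example Kauermann-Carroll) and a t reference on clinics minus clinic-level parameters. With baseline in the model, 12-month SBP as the outcome gives the same arm estimate. Then:

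- fix the covariate list before unblinding;
- delete the conditional clause in the last paragraph of section 9.3, and describe the randomization there as covariate constrained;
- label the unadjusted analysis and the adjustment for standardized differences above 0.1 as sensitivity analyses.

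If the sponsor prefers an unadjusted primary model, deleting the clause alone removes the ambiguity.

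The cost is SAP wording, with no new data. If four clinic variables prove non-prognostic, about 2-3 points of power are lost (82.9% to 80.7% with baseline SBP in the model; 77.9% to 75.4% without it). The gain from baseline SBP depends on the assumed ICC and slope and is negligible at an ICC of 0.01. The patient-level type I error of 6.1% is within about two Monte Carlo errors of 5%, but it is a reason to state the small-sample correction explicitly. The baseline encounter must also be defined consistently: section 6.2.2 identifies patients at their first visit to a trial clinic, while section 6.5 refers to the most recent qualifying encounter.

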#### 3.3 Study schema

## 4. Subject Selection

### 4.1 Inclusion Criteria

The trial will include provider subjects with eligible patients. Specific decision support at the point of care will also appear for patients whose latest outpatient/ambulatory blood pressures are elevated (i.e.,  $SBP \geq 140$  or  $DBP \geq 90$ ). There is no upper limit for SBP or DBP, as this cutpoint is driven by HEDIS criteria and would otherwise exclude patients who may be in greatest need of care. Limited inclusion criteria will be applied to maximize generalizability in accordance with pragmatic trial principles outlined by PRECIS-2 (Pragmatic Explanatory Continuum Indicator Summary). The patient population will only be included for the purpose of providers receiving decision support and for the purpose of analyzing the effect of the intervention. The study criteria are defined below.

**Provider-subjects** will receive EHR interventions if they are primary care providers (internal medicine, family medicine, geriatrics) employed by AAH at one of the 24 participating clinics cluster randomized to the intervention.

**EHR patient data will be collected retrospectively** for analysis and used for the EHR tools for providers based on the following criteria:

1. Medical Group Medical Home Population: 1 visit with PCP in past 2 years (rolling 24 months) and Patient has a medical group PCP as their EPIC General PCP
2. Current age 18-85 years

3. Hypertension diagnosis on EPIC Problem list OR at least 2 visits (office/telehealth/telephonic) with an encounter diagnosis of HTN on different dates, with at least one during the last 24 months (rolling dates)
4. Latest outpatient/ambulatory (exclude urgent care) SBP  $\geq 140$  or DBP  $\geq 90$  (12 months rolling) (lowest measure if more than one taken at the same time) (no upper limit)

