### **6.3 Schedule of visits**

There are no study-specific visits in this trial. We have outlined the time points in which data are collected below for implementation and evaluation of the interventions.

Data collection	Pre-randomization	Follow-up
EHR review for provider eligibility	X	
Provider characteristics (Demographics)	X	
Systolic blood pressure	X	X
Antihypertensive dosage	X	X
Resource use - Clinical encounters, using number of office visits, telephone calls and patient portal interactions	X	X

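### At the plan's ICC almost all the variance of a clinic mean lies between clinics, so a prespecified pre-launch clinic value of the outcome is a cheap possible gain in precision, if historical data show that it predicts

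*Combined protocol and SAP*

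**What the plan says.** The last paragraph of section 9.3 gives the default: "our primary analyses are planned as unadjusted". It makes one exception, for strong patient-level predictors that randomization leaves unbalanced. Earlier in 9.3 the primary model is a patient-level GEE with identity link and no named covariate. A second conditional rule repeats the analyses with adjustment for any baseline characteristic whose standardized difference between arms exceeds 0.1. That rule is not restricted to patient-level variables.

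Section 9.2 assumes "an intra-cluster correlation (ICC) of 0.1" and bases the sample size on "24 eligible primary care clinics including 537 providers and 49395 patients". It mentions no covariate.

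Section 5.2 uses clinic characteristics to constrain the randomization. The available text does not name them, and section 9.3 does not carry them into a model.

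On data, section 4.1 says "EHR patient data will be collected retrospectively". Section 6.3 introduces its table with "We have outlined the time points in which data are collected below for implementation and evaluation of the interventions", and the table marks systolic blood pressure both before randomization and during follow-up.

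**The concern.** With 24 clinics and about 2,000 patients in each, precision is set by how much clinics differ, not by the number of patients. More patients or more readings per patient change almost nothing. What can help, with the number of clinics fixed, is a variable that explains differences between clinics. A natural candidate is the same outcome in the same clinic before launch: the mean 12-month SBP change in a historical cohort selected by the trial's own rules. Treatment cannot have affected it, so it is a legitimate baseline covariate.

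No analysis in the plan names such a variable. At stake is precision in a trial whose power sits close to 80%. Some protection against chance differences between 12 clinics and 12 clinics is also at stake, but only for the part of those differences that the covariate predicts.

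**Working it through.** **Inputs (section 9.2).** Difference 5.0 mmHg ("We powered the study to detect a 5.0 mmHg mean change in SBP between the intervention arm and control arm"); SD 13.5; ICC 0.1; "an alpha threshold of 0.05", taken as two-sided because sidedness is not stated; 24 clinics; 49,395 patients. Section 5.2 allocates clinics equally, so 12 per arm. Equal clinic sizes are assumed throughout.

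**Reproducing the plan's power.**
- Mean clinic size m = 49,395/24 = 2,058.1.
- Design effect = 1 + (m − 1) × 0.1 = 206.7.
- Effective patients per arm = 24,697.5/206.7 = 119.5.
- SE of the difference = 13.5 × √(2/119.5) = 1.747 mmHg.
- Normal formula: Φ(5.0/1.747 − 1.960) = 81.7%. This agrees with the plan's claim of more than 80%.
- Noncentral t with 24 − 2 = 22 df: 78.1%.

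**Where the variance lies.**
- Between clinics: 0.1 × 13.5² = 18.225.
- Within clinics, for a clinic mean: 0.9 × 13.5²/2,058.1 = 0.080.
- Between-clinic share = 18.225/18.305 = 99.6%.

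**Effect of one clinic-level covariate.** Let r be the clinic-level correlation between the pre-launch and trial-period outcome. It is not in the documents, so a range is assumed. Two things change:
1. The clinic-mean variance is multiplied by (1 − r²), and the df fall to 24 − 3 = 21.
2. Under simple randomization the covariate differs between arms by chance. Estimating its slope therefore adds a factor of about 1 + 1/(24 − 4) = 1.05 to the variance.

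SE = √(2 × 18.305 × (1 − r²) × 1.05/12), with power from the noncentral t on 21 df. The last column is a simulation of the clinic-level analysis of covariance under simple randomization.

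| r (assumed) | SE, mmHg | Power, formula | Power, simulation |
|---|---|---|---|
| no covariate (22 df) | 1.747 | 78.1% | – |
| 0 | 1.790 | 75.9% | about 76% |
| 0.2 | 1.754 | 77.6% | about 78% |
| 0.3 | 1.707 | 79.7% | about 80% |
| 0.5 | 1.550 | 86.8% | about 87% |
| 0.7 | 1.278 | 96.1% | about 96% |

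Break-even against 78.1% is at r of about 0.23. Below that the covariate lowers power slightly. Counting only the lost degree of freedom would give 77.9% at r=0 and understate the cost about tenfold (0.2 points rather than about 2).

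**The case against.** The strongest reply is that nothing here is wrong. An unadjusted comparison in a randomized trial is valid, and the stated power reproduces under the normal formula. That stands. A reader might infer that the plan is in error, or that adjustment would certainly lift power well above 80% at almost no cost. The documents support neither inference: they give no r, the covariate loses power below about 0.23, and a clear gain needs r of roughly 0.4 to 0.5 or more.

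The outcome is also a change score, so each patient's identification SBP is already subtracted. Stable differences in clinic SBP level partly cancel, and r is likely to be lower for change than for level. An ICC from a single period does not show that clinic differences persist into the next. This stands, and it is why r should be estimated first.

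The constrained randomization may already balance prior clinic performance, because its characteristics are not named. That would reduce chance imbalance and the cost of the covariate. It would not by itself give the analysis the precision that adjustment gives.

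The rule on standardized differences above 0.1 could in principle admit a clinic-level variable. It names none, and it is triggered by observed imbalance and not by prognostic value.

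The data source is plausible but not shown. Sections 4.1 and 6.3 establish retrospective EHR data and pre-randomization SBP. They do not describe a historical cohort with both readings before launch.

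Finally, the need depends on the ICC: at an assumed 0.05, t-based power without any covariate is already 97%.

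**Conclusion.** The point holds as an inexpensive improvement. At the plan's own inputs 99.6% of clinic-mean variance is between clinics, and no planned analysis names the pre-launch clinic outcome. Against 78.1% unadjusted, the change in power runs from a loss of about 2 points (r=0) to a gain of about 9 (r=0.5) or 18 (r=0.7). This rests on an assumed r, ICC 0.1, equal clinic sizes, two-sided alpha and simple randomization. The cost would be smaller if the constrained randomization balances the covariate. Adjustment would remove only the part of chance clinic imbalance that the covariate predicts.

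**What to change.** 1. Before any trial outcome is seen, apply the trial's eligibility and outcome rules to historical EHR data, with both readings before launch, and compute each clinic's mean 12-month SBP change.
2. Do the same for a second pre-launch period and estimate r between the two. With 24 clinics this estimate is rough: at an observed 0.5, Fisher's z is 0.549 ± 1.96/√21, an interval for r of about 0.12 to 0.75. Report it with its interval.
3. If r is above about 0.25, prespecify this one number as a covariate in the primary GEE, with small-sample inference on 21 df. Keep the unadjusted model as a sensitivity analysis. If r is lower, leave the primary analysis as it is.
4. Name the constraining characteristics in 5.2, and reconcile that section with the reference to stratified randomization in 9.3.

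Cost: a historical query that can be released as clinic-level numbers, a sentence in 9.3, and about 2 points of power if the covariate proves useless. The query needs at least 12 months of pre-launch follow-up for the covariate, plus a second such period to estimate r.
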